The second study [72] enrolled 30 subjects aged 12 - 30 years (20 males and 10 females) in an 18-week, randomized, double-blind, placebo-controlled crossover trial. 11 subjects received 24 IU IN-OXT BID (16 years and older) or 18 IU BID (13 - 15 years). 18 subjects received 40 IU BID (16 years and older) or 32 IU BID (1315 years). The study found little impact on any of its outcome measures (Developmental Behavior Checklist Monitor, Parent, Teacher, and Adult; Yale-Brown Obsessive Compulsive Scale; The [name] Hyperphagia questionnaire; Reading the Mind in the Eyes Test; Epworth Sleepiness Scale and the Movie Stills). However, there was an increase in the number of temper tantrums (p = 0.023) on the higher doses of IN-OXT (40 and 32 IU), which could have been due to increased binding of oxytocin to V1a receptors and have resulted in increased aggression. This could also be bias against finding improvement on other behavioral measures.

[name] recently completed a double-blind, placebo-controlled crossover study of IN-OXT vs. Pbo in 24 children with PWS. Children were randomized to receive 5 days of either IN-OXT followed by placebo, or vice versa, with a minimum 4-week washout between the treatment periods. All children were in the Phase 2b or Phase 3 nutritional phase. Results revealed that all scales factor improvement from Day 3 to Day 6 favored oxytocin over placebo. In addition, after 5 days of treatment with IN-OXT, there was a 2.5 point decrease (i.e., improvement) on the Hyperphagia Questionnaire compared to a 1.6 point decrease on placebo. In addition, improvements were demonstrated on IN-OXT versus placebo on the ABC Factors of lethargy/social withdrawal, inappropriate speech, irritability, stereotypical behaviors and hyperactivity (107). Another recent multicenter trial using the oxytocin analogue carbetocin

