#### Titration Schedule:

Adverse events: Study physician will review with study participants regarding the nature,

duration and severity of noted adverse events. The study physician will make clinical judgements on the relationship between reported adverse events with study medication. If there is a high likelihood of adverse events being related drug effects, the subject will titrate down from 16 IU/day (4 sprays per day) to 12 IU/day (3 sprays per day) and will be reassessed in one week). At the next assessment the side effects and tolerability will again be reviewed by the PI and medical monitor. If the side effects have resolved, the subject will be titrated back up to 16 IU/day. If the side effects persist, the subject may continue on the 12 IU/day for another week; or will be discontinued from the study at the judgement of the PI. Subjects who do not receive the full dose by week four will be discontinued. Any subject who is discontinued from the study will be referred for continued medical follow up.

Lack of response: One upward titration will be allowed at week 2 to 24 IU/day (4 sprays per day) if study clinician, with consultation of the PI, determines that study subject experiences no response on hyperphagia via a categorical yes/no determination, and has no adverse events. In our current ongoing pilot study, and in [name]'s study, the initial hyperphagia response was observed at the week 1 and week 2 ratings.

**Instructions for Dosing:** Once the cap has been removed from the spray, the device should be held upright to the nostril and the actuator depressed. The patient should be in the sitting position and should be instructed to inhale gently through the nose while the actuator is being depressed. The head should be tilted back once the actuator is depressed to ensure that no fluid runs out of the nose. Parents may assist the child with dosing.

**Outcome Measures:** Project outcomes will be determined by changes in scores of parent and clinician rated measures from baseline to week 8 and comparisons of week 8 measures between active treatment and placebo groups. Assessments will be administered according to the schedule of events in **Table 2**.

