Safety monitoring will be completed at each visit in both remote and in-clinic settings. Participant will complete concomitant medication review, adverse event (AE) monitoring, ABC rating, and be monitored for hypogonadism, sleep apnea and lethargy, In addition, a complete physical and neurological exam and full panels of clinical labs (CBC, BMP, LFT, IGF-1, thyroid panel, lipid panel, HbA1C, testosterone, estrogen, growth hormone, ghrelin, pancreatic polypeptide, peptide YY, leptin, GLP-1, insulin and glucagon) will be completed at baseline and week 8 in person visits.

For participants who are able to provide salivary samples and co-operate with the collection process, the study team will attempt to obtain pre- and 1 hour post- study IP administration saliva at baseline, week4, and week 8 using the Oragene-Discover collection kit (ORG-500). The salivary samples will be used to measure patient oxytocin levels.

As required by the Division of Psychiatry Products and suggested by FDA review, we have also included the ABC-I subscale at every visit as a prospective assessment for suicidal ideation. The ABC will also be used to assess for adverse events, including increased aggression or temper tantrums. Urine pregnancy tests will be completed at every visit to ensure subject safety. If a subject becomes pregnant during the study, she will immediately be discontinued from the medication. All subjects must use abstinence or a valid method of non-estrogen based double barrier contraception to participate in the study.

While some of these secondary measures have not been studied in PWS, we believe that they

are appropriate for this population as a valid measure of treatment efficacy and focus on important target issues of PWS – including repetitive behaviors (Repetitive Behavior Scale-Revised). The WHOQOL is a validated measure used to assess quality of life and has been used in a vast array of clinical trials in varied disorders (muscular dystrophy, hypertension, tuberculosis, etc.). The Caregiver Strain questionnaire (CSQ) is a commonly used and well-validated self-report questionnaire developed to assess caregiver strain for families with a child living with an emotional or behavioral disorder. The ABC has been used to assess disruptive behaviors in other disorders such as Down Syndrome and other intellectual disabilities

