#### **Safety Measures:**

Aberrant Behavior Checklist – Irritability (ABC-I): The ABC is an informant rating instrument that was empirically derived by principal component analysis to measure behavior in those with developmental disability and ASD. It contains 58 items that resolve into 5 subscales. The subscales and the respective number of items are as follows: (a) irritability – 15 items, (b) lethargy/social withdrawal – 16 items, (c) stereotypic behavior – 7 items, (d) hyperactivity/noncompliance – 16 items, and (e) inappropriate speech items. The ABC was designed to be completed by any adult who knows the patient well, such as a parent/caregiver or teacher. This instrument measures behavior on a four point severity scale where 0 = no problem at all, 1 = behavior is a problem but in a slight degree, 2 = problem is moderately serious, and 3 = problem is severe in degree. As suggested by the FDA, we have included the

ABC-I subscale as a prospective assessment for suicidal ideation and behavior at every visit. Given the concern over the possibility of increased temper tantrums raised by a previous study of high dose IN-OXT in the PWS population, the ABC-I can also inform investigators if there are any trends towards increased irritability and disruptive behavior. The Division of Psychiatry Products (DPP) has developed a policy that all clinical protocols for products developed in DPP, whatever the indication, include a prospective assessment for suicidal ideation and behavior. Per the DPP, these assessments need to be included in every clinical protocol at every planned visit and in every phase of development. Collecting this data ensures that patients in clinical trials who are experiencing suicidal ideation or behavior are detected and adequately managed. This is important whether or not a particular drug is associated with treatment-emergent suicidal behavior. As per the recommendation of the FDA, in studies of subjects with ASD, investigators frequently use the ABC-I subscale to fulfill this requirement. The ABC may help identify any increased risk to self through observation rather than self-report. In particular, the ABC-I can be useful for obtaining information about treatment-emergent irritability, self-injurious behavior or worsening of aggressive behavior. The ABC will be completed at every visit and requires approximately 25 minutes.

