#### **Detailed Description of Analyses**

**Primary Analyses**: Analyses for Specific Aim (1): To compare IN-OXT vs. placebo with respect to improvement in the hyperphagia severity in children with PWS via improvement in scores on the Hyperphagia Questionnaire-Clinical Trials.

The primary analysis will evaluate the hypothesis that IN-OXT will decrease hyperphagia vs. placebo.

- 1. Response to treatment will be assessed in two ways:
  - a. The effects of IN-OXT on hyperphagia will be analyzed using an intent-totreat approach with the two-sample T-test or Wilcoxon rank sum tests to compare treatment groups at specific visits as well as linear mixed effects models to analyze the repeated measures and changes over time.
  - b. The proportion of responders in each treatment group will also be compared. Response will be defined as a 30% or greater decrease in food-seeking and eating behaviors from baseline on the Hyperphagia Questionnaire-Clinical Trials. Dropouts for clinical reasons will be coded as non- responders. Differences in the proportion of responders in each treatment group will be evaluated using the chi-square test and time to response will be assessed using survival analytic techniques.
  - c. All tests will be two-tailed with an alpha level of 0.05.

**Secondary Analyses:** Analyses for Specific Aims (2) through (8): To compare IN-OXT vs. placebo in children with PWS on change in:(2) Repetitive behaviors via scores on the Repetitive Behavior Scale – Revised (RBS-R) and Montefiore-Einstein Rigidity Scale-Revised (MERS-PWS)(3) Weight and body composition via impedance analysis. (4) Quality of Life Measures on the World Health Organization Quality of Life Scale (WHOQOL)(5) Clinical Global Impression Scale (CGI-I) (6) Salivary Oxytocin Concentration (7) Safety Analyses

IN-OXT and placebo groups will be compared to the above secondary measures will be analyzed using methods similar to those outlined above. Associations between outcome measures at a specific time point will be analyzed with the Spearman rank or Pearson correlation coefficient.

- 1. Secondary Aim (1) Repetitive Behaviors
  - *a.* The effects of treatment on frequency and severity of repetitive behaviors will be assessed by fitting linear mixed effects models to the data on the RBS-R scores. We hypothesize that IN- OXT will significantly reduce repetitive behaviors from baseline to endpoint compared to Placebo.

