  - b. The relationship between frequency of suicidal behaviors will be assessed on the ABC-I to evaluate whether IN-OXT vs. placebo is associated with a change in the irritability subscale of the ABC-I which serves as a surrogate for suicidal ideation in this population.

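### The ABC irritability score has only an arm-level analysis: no count of children who worsened, and no rule for children who leave because of behaviour

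*Combined protocol and SAP*

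**What the plan says.** Purpose of the measure. The Outcome Measures text states: "The ABC will also be used to assess for adverse events, including increased aggression or temper tantrums". Under Safety Measures, because tantrums were raised by an earlier high-dose study in PWS, "the ABC-I can also inform investigators if there are any trends towards increased irritability and disruptive behavior". The section on previous studies in PWS reports that in that trial "there was an increase in the number of temper tantrums (p = 0.023) on the higher doses of IN-OXT".

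Timing. "The ABC will be completed at every visit and requires approximately 25 minutes". The Schedule of Events shows a pre-dose baseline and weeks 2, 4, 6, 8 and 10.

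Analysis. Secondary Aim (5) item b is meant "to evaluate whether IN-OXT vs. placebo is associated with a change in the irritability subscale of the ABC-I", and presents the subscale as a surrogate for suicidal ideation. The introduction to the Secondary Analyses, whose list includes safety, says that "the above secondary measures will be analyzed using methods similar to those outlined above". Those methods are two-sample tests at visits, change from baseline to week 8, and linear mixed models. The Missing data section bases the primary analysis on the data available at each time point.

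Exits. The Titration Schedule says of adverse events: "If the side effects persist, the subject may continue on the 12 IU/day for another week; or will be discontinued from the study", the latter at the judgement of the PI.

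Contrast with benefit. For the HQ-CT the plan defines a per-child response (a fall of 30% or more) and codes clinical dropouts as non-responders. The ABC has no counterpart for worsening.

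**The concern.** The protocol gives the ABC two safety jobs, suicidality and aggression or tantrums. Only the first has a stated analysis, and that is an arm-level change. Behavioural worsening may affect some children and not others: the background reports improved irritability on oxytocin in the short crossover trial in children, but tantrums in one underweight child at 0.5 IU/lb. An average sets improvers against worseners. Because side effects can lead to discontinuation from the study, some of the most affected children may have no week-8 score.

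At stake is whether a flat or improved mean irritability score could be carried into Phase 3 planning as evidence of behavioural safety while a fraction of treated children became clearly worse.

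**Working it through.** **The plan's own figure.** 25 per arm, d = 0.8, two-sided 5%: n = 2(1.960 + 0.842)²/0.8² = 24.5, so 25 per arm. Power is 0.807 by the normal formula and 0.791 by exact noncentral t. The stated 80% reproduces.

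**Inputs that the documents do not give.** The SD of ABC-I change, the share of children who worsen, the size of worsening and the exit rate are all assumed below.

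**Dilution, in SD units.** Let a share f of the active arm worsen by k SD, and a share q of those children leave before week 8.
- Full shift = f × k = 0.20 × 2 = 0.40 SD, half of the 0.8 SD used for sizing.
- With half leaving: 0.10/0.90 × 2 = 0.22 SD. With all leaving: 0.
- Worsening in a subgroup also widens the active arm: variance 1 + k²f(1 − f) = 1 + 4 × 0.16 = 1.64. The standard error is √((1.64 + 1)/25) = 0.325, and 0.40/0.325 = 1.23, well below 1.96.

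Simulated chance of a significant adverse result (4,000 trials, 25 per arm). The proportion endpoint uses a cut-off of 1.5 to 2 SD and counts exits as worsened:

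| Affected children leaving | Week-8 t-test | Proportion worsened, chi-square | Same, Fisher |
|---|---|---|---|
| none | 0.21 | 0.20–0.26 | 0.05–0.13 |
| half | 0.10 | 0.37–0.44 | 0.17–0.22 |
| all | 0.025 | 0.47–0.64 | 0.30–0.37 |

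With all retained, week-8 power runs from 0.07 (f = 10%, k = 1.5) to 0.61 (f = 30%, k = 3).

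**By visit, in points.** Assumed: SD of change 6, within-child correlation 0.6, mean improvement 2 in both arms, 30% of treated children 10 points worse from week 4, leavers contributing weeks 2 and 4 only. The true week-8 difference is 0.30 × 10 = 3.0 points. With half of the affected leaving, the observed one is 0.15/0.85 × 10 = 1.8. With all leaving it is 0. The proportion column uses an assumed margin of 8 points, with 6 to 10 points in brackets:

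| Affected children leaving | Week-8 test | Week-4 test | Worst change | Proportion worsened, chi-square |
|---|---|---|---|---|
| none | 0.33 | 0.33 | 0.35 | 0.36 (0.31–0.38) |
| half | 0.15 | 0.31–0.34 | 0.26 | 0.47 (0.36–0.57) |
| all | 0.02–0.03 | 0.31–0.34 | 0.19 | 0.59 (0.44–0.75) |

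A mixed model (250 trials per cell, so approximate) keeps part of the signal. With half leaving its power is about 0.23. With all leaving it is about 0.06 to 0.08, with a week-8 estimate near 1.1 points against the true 3.0.

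In both simulations only affected treated children leave. Part of the gain from counting exits as worsened is therefore built in; unrelated or placebo exits would shrink it.

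**Worst post-baseline change as the summary.** With no drug effect and 30% of the active arm leaving early, the maximum over visits favours oxytocin by about 0.5 points, because it is taken over fewer visits.

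**Adverse-event comparison.** At 25 per arm, 5% versus 20% has power 0.36 (exact chi-square 0.38, Fisher 0.20) and would need 76 per arm for 80%. About 10% versus 45% is needed for 80% power.

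**The case against.** The strongest reply is that tantrums are not judged by the ABC-I mean alone. Item a of the same aim compares rates of specific side effects and other adverse events between arms. The Safety Analyses section tabulates treatment-emergent events by maximum severity per patient, by relation to drug, and where they led to stopping study drug. A child removed for tantrums is counted there. If every affected child were logged, with 5% on placebo, that comparison would have power of about 0.70 at 30% affected and 0.90 at 40%, whatever the exits. This stands as partial cover. It depends on each tantrum being judged an adverse event, in a syndrome whose background section lists tantrums as characteristic behaviour, and no ABC score is given for that judgement.

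Second, a reader might infer that the plan looks only at a week-8 mean, and take 3% versus 19% (week-8 test against worst change, 30% affected, all leaving) as what the plan loses. The documents do not support that. Item b names neither a mean nor week 8, tests are planned at specific visits, and mixed models use scores recorded before exit. In the scenario above the week-4 test does better than worst change. The contrast is an upper bound against the week-8 test alone, and the week-4 result itself relies on worsening being present by week 4 and on leavers attending that visit.

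Third, a reader might infer that children are taken off study for tantrums by rule. The titration text speaks of side effects in general and does not name tantrums.

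Fourth, the borrowed methods include a responder proportion. But that responder is defined as improvement on the HQ-CT, and nothing translates it into worsening on the ABC.

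Last, lethargy is not ignored: it sits in the adverse-event row of the schedule and can enter the rate comparison. Only the ABC lethargy subscale lacks a stated analysis.

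**Conclusion.** The concern holds in a limited form. The ABC is collected at every visit partly to detect behavioural worsening, yet its only stated analysis is an arm-level change, with no per-child definition of worsening and no rule for children who leave because of behaviour. The HQ-CT benefit endpoint has both.

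Under assumed inputs, 20% of treated children worsening by 2 SD would be detected at week 8 with probability 0.21 or less, falling to 0.025 if all of them leave. By-visit tests, mixed models and the adverse-event tables reduce this loss, so the plan cannot be said to average the harm away altogether.

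A proportion worsened gains most where affected children leave (0.47 and 0.59 against 0.15 and 0.02 for the week-8 test at 30% affected, half and all leaving, 8-point margin). If none leaves, there is no clear gain. With 25 per arm its value is mainly descriptive. The point is worth fixing because the data already exist and the change is small.

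**What to change.** In Secondary Aim (5) item b:
- Keep the by-visit and mixed-model analyses of change.
- Add, per arm, the number and percentage of children whose ABC-I worsened from the pre-dose baseline at any post-baseline visit by at least a stated margin. The sponsor should justify the margin and fix it before unblinding. State whether the week-10 follow-up counts.
- Count children who leave the study because of behavioural adverse events as worsened, parallel to the HQ-CT dropout rule.
- Give an exact confidence interval for the difference between arms.
- Optionally, show the same count descriptively for the ABC lethargy subscale.

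Do not make worst post-baseline change the main summary: a maximum over fewer visits is lower by construction and can mask harm when exits differ by arm. The any-visit count shares this weakness for exits unrelated to behaviour, so report visits attended by arm beside it.

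The cost is SAP wording and one table from data already collected. The downside is that the margin is a judgement for which the documents give no figure, and the interval will be wide at this sample size.

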Measurements obtained at a specific time point (e.g. 8 weeks) will be compared between the IN-OXT and placebo groups with the two sample t-test or Wilcoxon rank sum test. In addition, the change in outcome measures between baseline and 8 weeks will be compared between

treatment groups. Exploratory analyses will first be performed to evaluate whether the magnitude of changes in these variables between the two time points depends on the baseline value. If there is no evidence that change is dependent on baseline, then two sample tests will be used to compare the mean change in each variable between treatment groups; otherwise, analysis of covariance models will be fit to the data where the outcome is the level measured at 8 weeks, and the main effects are treatment group and baseline value [15;37]. Adjustment for any patient characteristics which appear to be imbalanced across treatment groups will be accomplished by including the relevant terms as additional covariates into the model. To compare longitudinal trends in outcomes between treatment groups, linear mixed effects models will be fit to all repeated measures obtained during follow-up, with main effects for time and treatment group and a time x treatment interaction term; this is a widely used statistical approach in longitudinal studies of psychiatric outcomes. Appropriate data transformations, such as the log transform, will be applied if the data deviate from the normal distribution. Although a number of different outcomes will be analyzed, we will not adjust for multiple testing given the exploratory nature of this study.

Additional subgroup analyses will also be performed to evaluate and compare treatment effects in males and females. Given the limited sample size of this Phase 2 trial, however, any subgroup analyses will be viewed as exploratory.

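### Safety item b is framed as the frequency of suicidal behaviours but compares change in the whole ABC irritability subscale, which is insensitive to a few affected children and cannot separate suicidality from irritability

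*Combined protocol and SAP*

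**What the plan says.** Under Detailed Description of Analyses, Secondary Aim (5), item b opens: "The relationship between frequency of suicidal behaviors will be assessed on the ABC-I". What it then does is ask whether treatment is associated with a "change in the irritability subscale of the ABC-I which serves as a surrogate for suicidal ideation in this population". It gives no item set, per-child threshold, count or listing.

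Item b names no test. Safety Analyses is on the list of secondary analyses, and for that list the plan says the "above secondary measures will be analyzed using methods similar to those outlined above". Those methods are the t-test or Wilcoxon test at visits, mixed models and, in the Summary of Analytic Approach, a rule for change from baseline. If change does not depend on the baseline value, "two sample tests will be used to compare the mean change in each variable between treatment groups"; otherwise ANCOVA is used. On the error rate: "All tests will be two-tailed with an alpha level of 0.05".

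The Safety Measures section describes the irritability subscale as 15 items, each scored 0 to 3, and says it informs on irritability, self-injury and aggression. It gives the reason for collecting the scale in individual terms: "Collecting this data ensures that patients in clinical trials who are experiencing suicidal ideation or behavior are detected and adequately managed". Table 2 schedules the full ABC before dosing at baseline and at every later visit.

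**The concern.** The quantity named (how often suicidal behaviour occurs) and the quantity analysed (change in a broad behaviour score) are different.

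The score can also move for other reasons. In the review of earlier oxytocin studies in PWS, the paediatric crossover is described so: "improvements were demonstrated on IN-OXT versus placebo on the ABC Factors of lethargy/social withdrawal, inappropriate speech, irritability". The same review reports more temper tantrums at higher doses in another trial (p = 0.023). The protocol uses the ABC to watch for tantrums and aggression too, so one score has to answer two safety questions that it cannot tell apart.

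At stake is how item b will be read. A fall in average irritability could be reported as reassurance on suicidality while a few children have new self-injury. A rise in tantrums could be reported as a suicidality signal with no such event behind it.

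**Working it through.** **The plan's own figure.** Power Analysis states 80% power at d = 0.8 with 25 per arm, two-sided 5%. The t-test gives 79.1% and the normal approximation 80.7%, so the figure is reproduced. At 80% power, 25 per arm detects d = 0.81. No power is given for item b.

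**Inputs from the documents.** 25 per arm; 15 items scored 0 to 3, so a range of 0 to 45; two-sided alpha 0.05.

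**Assumptions, because the documents give no figures.** SD of ABC-I change 5 to 10 points. New self-injury adds up to 9 points for an affected child (three items going from 0 to 3; the number of self-injury items is not stated). Affected children are in the oxytocin arm only.

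**Detectable difference in points.** 0.81 x 5 = 4.0 and 0.81 x 10 = 8.1. A difference of 4 to 8 points is needed for 80% power.

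**Shift produced by affected children.** Shift = k x rise / 25.
- k = 1: 9/25 = 0.36 points
- k = 3: 27/25 = 1.08 points
- k = 5: 45/25 = 1.80 points

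**Chance that the t-test is significant in the harm direction.** Simulation: normal changes, 9 points added to k treated children, 100,000 trials per row. With no effect at all this chance is 2.5%.

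| SD | 3 of 25 affected | 5 of 25 affected |
|---|---|---|
| 5 | 9% | 17% |
| 8 | 6% | 10% |
| 10 | 5% | 8% |

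The Wilcoxon alternative does no better. With 3 affected it is significant, in either direction, in 5% to 8% of trials.

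**Masking by an irritability benefit.** Three affected children add 27 points in total, which is cancelled if the other 22 improve by 27/22 = 1.23 points each. Suppose instead that every treated child gains a benefit B, with SD 8 and 3 affected. The chance that the oxytocin mean is still the better one is Φ[(B - 1.08) / (8 x √(2/25))], where 8 x √(2/25) = 2.26.
- B = 2: Φ(0.41) = 66%
- B = 3: Φ(0.85) = 80%

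**What a count shows.** 3/25 against 0/25 is 12%, exact 95% CI 2.5% to 31%. As a test it is weak too: Fisher p = 0.23, uncorrected chi-square p = 0.074. With 0/25 observed, the upper 95% limit is still 13.7%.

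**Background noise in a count without a threshold.** There are five post-baseline visits (weeks 2, 4, 6, 8 and 10). If chance raises an item score at 5% of visits (assumed, independent), 1 - 0.95^5 = 23% of children are flagged with no drug effect, about 6 of 25 per arm.

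**The case against.** **Individual cases are handled elsewhere.** This largely stands, and it limits the point to item b. A reader might infer that self-injury could pass unseen through the whole trial; the documents do not support that. The Safety Analyses section lists all AEs and tabulates treatment-emergent AEs by preferred term and arm. Item a compares AE rates by chi-square. Review is provided by the safety monitor at least monthly, by the medical monitor after each visit (Risks) and by the DSMC. This route does depend on the behaviour being reported as an AE, and none of the six additional AE summary categories is suicidality or self-injury. The promised summary of suicidal evaluation has no defined source. The RBS-R has a self-injurious behaviour subscale, but the plan does not link it to this analysis.

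**The plan does not say mean in item b.** Correct. The method is inferred from the general strategy, which also offers the Wilcoxon test and, for the primary outcome, a responder proportion. But no responder rule is defined for the ABC-I, and the rank test is no more sensitive here.

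**The FDA suggested the ABC-I.** As the protocol describes it, the request is for prospective assessment and detection at every visit. It would be tempting to conclude that the request goes unmet. The documents do not support that either, since nothing in them ties the request to an arm comparison. The instrument is not at issue.

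**A count has its own faults.** It does: a between-arm test of it is weak at this sample size, and any-increase counting is noisy in a population with skin picking. The count should therefore be descriptive, with a severity threshold and both arms shown.

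**Conclusion.** The point holds for item b. As written, the suicidality analysis compares arms on a score that mixes three kinds of behaviour and never counts the one it names. Under the stated assumptions it flags 3 affected children of 25 in about 5% to 9% of trials and 5 of 25 in about 8% to 17%. With a 2 to 3 point general irritability benefit (SD 8), the arm mean favours oxytocin in 66% to 80% of trials despite 3 affected children.

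The exact percentages rest on the assumed SD, the 9-point rise and the one-sided split of cases. Much of the low detection rate comes from having 25 per arm, so it should not be read as showing that another test would succeed. The mismatch between the stated and analysed quantities needs no assumption. It is worth correcting before unblinding, but it is not a failure of the safety plan as a whole.

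**What to change.** In Secondary Aim (5), item b:

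1. Label the ABC-I score comparison as an irritability and tantrum outcome, and do not read it as the frequency of suicidal behaviour.
2. Add a by-arm count of children, with risk difference, exact 95% CI and a patient listing, showing two components separately:
   - children with an AE coded as suicidal or self-injurious;
   - children who worsen from the pre-dose baseline on the ABC-I self-injury items, with the items and a severity threshold fixed before unblinding (for example, a new score of 2 or more, or an increase of 2 or more).
3. Show both arms, so that background fluctuation and skin picking are visible, and present the results descriptively without a significance test.

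The cost is a wording change and one extra table with its listing. The full ABC is already collected at baseline and at every later visit, so no new assessment is needed. The intervals will be wide, which reflects what 25 children per arm can show.
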